9.0 Safety Analyses

9.1 General Considerations

Safety analyses will include reporting of adverse events, laboratory, and vital signs measurements. Safety analyses will be carried out using the Safety Analysis Set for both continued and terminated groups except for mean change from baseline analysis of laboratory and vital signs, which will be provided for continued groups only.

All summaries of adverse events will be provided using data through Week 24, through Week 48 and through Week 48 per 100 patient-years.

The following summary statistics will be presented for subjects who have both baseline and post-baseline values for laboratory parameters and vital signs: the mean value at baseline and at each respective protocol specified visit, and the mean, standard deviation and median for changes from baseline. Categorical data will be summarized using frequencies and percentages. The number of non-missing values will be given.

For the safety analyses, subjects are assigned to a treatment group based on the treatment actually received, regardless of the treatment randomized. A subject's actual treatment will be determined by the most frequent dose regimen received.

For the safety analyses, baseline is defined as the last measurement prior to the first dose of study drug.

Missing safety data will not be imputed.

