9.3 Analysis of Laboratory Data

Data collected from central and local laboratories, including additional laboratory testing due to an SAE, will be used in all analyses, except for baseline, where SAE-related laboratory assessments on or before the first dose of study drug will be excluded. The clinical laboratory tests defined in the protocol operations manual (e.g., hematology and clinical chemistry) will be summarized.

For the analysis of laboratory data, values observed up to 30 days after the last dose of study drug will be included.

Each laboratory variable will be summarized for all time points (starting with baseline) with the number of non-missing observations, mean and standard deviation, median, minimum and maximum.

For continued groups, mean change from baseline to each applicable post-baseline visit will be summarized for selected laboratory variables, with the number of observations, baseline mean, and visit mean. The change from baseline mean, standard error, and 95% confidence interval will be presented for the mean change from baseline within each treatment group and difference between treatment groups.

Shift tables will be provided for each hematology, clinical chemistry parameter. Shifts from Baseline to the following endpoints will be considered: post-Baseline value and final value. This analysis will be performed only for category of "low or normal" at Baseline which shift to 'high' and category of "high or normal" at Baseline which shift to category of 'low.'

For selected laboratory variables including hemoglobin, neutrophils, lymphocytes, platelets, leukocytes, creatinine, ALT, AST, bilirubin, CPK, a listing of all observations collected will be generated for subjects that had at least one post-baseline observation meeting pre-defined criteria for potentially clinically important values. The number and percentage of subjects in each treatment group who have at least one post-baseline observation meeting the pre-defined criteria for potentially clinically important values will be provided for each variable. The criteria for potentially clinically important laboratory values will be determined by NCI CTCAE version 4.03 of greater than Grade 3 or greater than Grade 4.

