9.4 Analysis of Vital Signs

Vital sign measurements of systolic and diastolic blood pressure, pulse rate, body temperature, and weight will be summarized.

For the analysis of vital sign data, values observed up to 30 days after the last dose of study drug will be included.

Each vital sign variable will be summarized for all time points (starting with Baseline) with the number of non-missing observations, mean and standard deviation, median, minimum and maximum.

For continued groups, mean change from baseline to each applicable post-baseline visit will be summarized for each vital sign variable, with the number of observations, baseline mean, and visit mean. The change from baseline mean, standard error, and 95% confidence interval will be presented for the mean change from baseline within each treatment group and difference between treatment groups.

Vital sign variables will be evaluated based on potentially clinically important (PCI) criteria ([Appendix C](#)). For each vital sign PCI criterion, the number and percentage of subjects who have a vital sign value meeting the criteria will be summarized. Listings

will be provided to summarize subject-level vital sign data for subjects meeting PCI criteria.

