11.2.4 Safety Analyses

Safety Analysis specified in this SAP will be included in the interim analysis except summary of other baseline characteristics listed in Section 7.1:

The following safety results will be summarized in the interim analysis:

- Overview of TEAEs (treatment emergent adverse events).
- TEAEs by SOC (system organ class) and PT (preferred term).
- Treatment-emergent SAEs (serious adverse events) by SOC and PT.
- TEAEs leading to study drug discontinuation by SOC and PT.
- TEAEs by SOC and PT and maximum relationship to study drug.
- TEAEs by SOC and PT and maximum toxicity grade.
- AESIs (adverse events of special interest) by SOC and PT.
- Listing of Pre-treatment SAEs.
- Listing of SAEs.
- Listings of AESIs.
- Listing of Aes leading to death.
- Listing of Aes leading to study drug discontinuation.

- Analysis of mean change from baseline in laboratory and vital sign variables.
- Summary of potentially clinically significant laboratory and vital sign variables.
- Listings of potentially clinically significant laboratory and vital sign variables.
- Shift tables for laboratory and vital sign variables.

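### The SAP drops mean change from baseline in laboratory values and vital signs, with its 95% CI against placebo, for any arm terminated after the interim analysis

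*SAP*

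**What the plan says.** SAP 9.1 starts from a general rule, "Safety analyses will be carried out using the Safety Analysis Set for both continued and terminated groups", and then makes one exception: "except for mean change from baseline analysis of laboratory and vital signs, which will be provided for continued groups only".

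The detailed sections carry the exception through. SAP 9.3 reads "For continued groups, mean change from baseline to each applicable post-baseline visit will be summarized for selected laboratory variables", and SAP 9.4 reads "For continued groups, mean change from baseline to each applicable post-baseline visit will be summarized for each vital sign variable". Both sections show what the restricted analysis contains: a "95% confidence interval will be presented for the mean change from baseline within each treatment group and difference between treatment groups".

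Three other places bear on the point.

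- A later paragraph of SAP 9.1 promises, for subjects with both baseline and post-baseline laboratory and vital-sign values, "the mean, standard deviation and median for changes from baseline". It sets no limit by group.
- Protocol 7.4 plans a summary of mean change for selected laboratory and vital-sign parameters with no arm excepted. It calls the analysis descriptive. Protocol 7.1 allows the safety analysis to be revised after the decision of the Internal Executive Review Committee (IERC).
- SAP 11.2.4 lists, among the interim outputs, "Analysis of mean change from baseline in laboratory and vital sign variables", again with no arm left out. SAP 11.2.1 sets the interim cutoffs at 7 July 2021 for the first half of the planned subjects and 20 June 2021 for the rest.

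**The concern.** The main objective covers the safety of each regimen against placebo and the choice of dose for further development. The five arms (placebo, each drug alone, and two upadacitinib doses in combination) allow a laboratory effect to be traced to a component or to the upadacitinib dose. Leaving an arm out of the mean-change analysis breaks some of those contrasts, although the data have been collected under randomisation and blinding.

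Mean change is also the planned output best suited to showing a moderate shift across a whole arm. Lipids are an example. They are measured (Operations Manual 3.13), and Protocol 2.2 names hypercholesterolemia as possibly related to upadacitinib. They are not among the variables for which SAP 9.3 counts potentially clinically important values. For a terminated arm they would have by-visit summaries and shifts between categories, but no estimated difference from placebo. This assumes that lipids are among the selected variables for mean change, which SAP 9.3 does not list.

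Protocol 7.5 ties the interim analysis to the treatment regimens and to benefit/risk for rollover, and Protocol 5.5 gives relevant toxicity as one possible ground for stopping. If an arm were stopped on safety grounds, it would be the arm whose laboratory effects most need an estimate. The SAP gives no reason for the exception.

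**Working it through.** **1. The plan's own figure.** The documents give no figure on this point. The nearest is the sample size statement (SAP 2.4): 65 per arm, placebo response 25%, difference 20% to 25%, two-sided alpha 0.10, power 78% to 91%. With the pooled-variance test and no continuity correction:

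- Response 45%: SE under the null = sqrt(2 × 0.35 × 0.65/65) = 0.0837; SE under the alternative = sqrt((0.25 × 0.75 + 0.45 × 0.55)/65) = 0.0818; power = Φ((0.20 − 1.645 × 0.0837)/0.0818) = 77.7%.
- Response 50%: SEs 0.0849 and 0.0820; power = Φ((0.25 − 1.645 × 0.0849)/0.0820) = 91.1%.

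The stated power reproduces. It serves here only to fix the planned 65 per arm.

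**2. What a terminated arm keeps and loses (laboratory, vital signs, ECG).**

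| Output | SAP section | Terminated arm | Between-group difference with CI specified |
|---|---|---|---|
| n, mean, SD, median, range by visit | 9.3, 9.4 | kept | no |
| Laboratory shift tables | 9.3 | kept | no |
| Counts of potentially clinically important values | 9.3, 9.4, Appendix C | kept | no |
| Liver-test thresholds | 9.3 | kept | no |
| QTcF above 500 msec | 9.6 | kept | no |
| Mean change from baseline | 9.3, 9.4 | dropped | yes, 95% CI |

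Adverse events, including those of special interest, are also kept. The exclusion therefore removes one output, and it is the only one in the table with a specified estimate against placebo.

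**3. The two paragraphs of SAP 9.1.** The first withholds mean change from terminated arms. The later one requires the mean, SD and median of change for anyone with paired values. A programmer cannot satisfy both for a terminated arm. Even if the later paragraph prevails, it supplies descriptive change statistics only, with no difference from placebo and no CI.

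**4. What the interim analysis supplies.** Its main safety set is everyone dosed before 20 June 2021 (SAP 11.2.1), and mean change is planned for all arms. It stops at the mid-2021 cutoffs, so later data from a terminated arm never enter this analysis.

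**5. Precision if the contrast is restored.** For two arms with n each and a common SD of change, the 95% half-width is 1.96 × sqrt(2/n) SD. The n at a given visit is an assumption, ranging from about half the planned arm to all of it.

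- n = 65: 1.96 × sqrt(2/65) = 0.34 SD
- n = 33: 1.96 × sqrt(2/33) = 0.48 SD
- n = 32: 1.96 × sqrt(2/32) = 0.49 SD
- Terminated arm 32, placebo 65: 1.96 × sqrt(1/32 + 1/65) = 0.42 SD

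**The case against.** A reader might infer that terminated arms can no longer be compared with placebo on laboratory safety. The documents do not support that. The kept outputs allow comparison, and by-visit n, mean and SD let anyone compute an unadjusted difference in visit means with a CI. That stands. It is a weaker substitute: those summaries are not limited to subjects with paired values, make no allowance for baseline, and are less precise than change whenever the baseline-to-visit correlation exceeds 0.5 (variance σ² against 2σ²(1 − ρ)).

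Nor are the remaining counts confined to extreme values. Liver criteria begin at 3 × ULN for ALT and AST and 1.5 × ULN for alkaline phosphatase, the weight criterion is a 7% change, and laboratory shift tables record moves out of the normal range. This stands.

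A reader might call the exception a breach of the protocol. It is not one: Protocol 7.1 permits revision after the IERC decision, and Protocol 7.4 promises descriptive mean change, not a between-arm difference or CI.

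A reader might also infer that an arm was stopped for a laboratory signal that the exception now hides, or that the date of SAP version 3.0 (17 December 2021, after the interim cutoffs) shows that interim results drove it. SAP 11.2 states termination only as a possibility. The protocol reports an IERC decision and an adjustment of treatment groups, but no document names a stopped arm or gives a reason. Stopping for lack of efficacy fits equally well, and the study team stays blinded until the Week 24 Primary Analysis.

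Finally, subjects in a terminated arm return for a premature discontinuation visit and then have only a phone call (Protocol 5.5), so later visits will be thin. This stands, and is why a single figure of 0.34 SD would be a best case. In the meantime, the data monitoring committee conducts quarterly unblinded safety reviews.

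**Conclusion.** The point holds as a minor but real gap. For any arm terminated after the interim, the Primary and Final Analyses would give no planned mean-change contrast with placebo in laboratory values or vital signs. The exception has no stated reason, departs from Protocol 7.4 as to mean change itself, and conflicts with another paragraph of SAP 9.1. Only that contrast is lost.

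Its size is the missing estimate for up to 65 subjects per terminated arm, with a half-width of 0.34 SD at best and 0.48 to 0.49 SD if about half of each arm contributes. These figures assume a common SD of change, a normal approximation and no covariate adjustment. The point has practical effect only if at least one arm was terminated. Which component or dose contrasts are affected depends on which arm that was, and the documents do not say.

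**What to change.** Delete the exception in SAP 9.1 and the continued-groups qualifier in SAP 9.3 and 9.4. This also reconciles the two paragraphs of 9.1. For terminated arms, report mean change and the difference from placebo with 95% CI, using values up to 30 days after last dose (the window already set in 9.3 and 9.4), and print n at each visit. State how values from the premature discontinuation visit are assigned to scheduled visits. If the sponsor prefers to keep the exception, the SAP should give the reason and say whether the later paragraph of 9.1 applies to terminated arms.

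The cost is small: extra columns in tables already specified for the continued arms and for the interim, and imprecise estimates at later visits. No new data are needed.

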9.2 Adverse Events

Adverse events (AEs) will be summarized and presented using primary MedDRA System Organ Classes (SOCs) and preferred terms (PTs) according to the version of the MedDRA coding dictionary used for the study at the time of database lock. The actual version of the MedDRA coding dictionary used will be noted in the AE tables and in the clinical study report. Specific adverse events will be counted once for each subject for calculating percentages, unless stated otherwise. In addition, if the same adverse event occurs multiple times within a subject, the maximum toxicity grade and level of relationship to investigational product will be reported.

9.2.1 Treatment-Emergent Adverse Events

Treatment-emergent Adverse Events (TEAE) are defined as any AE that begins either on or after the first dose of study drug in M19-130 and within 30 days after the last dose administration of the study drug in M19-130.

Events where the onset date is the same as the study drug start date are assumed to be treatment-emergent. If an incomplete onset date was collected for an adverse event, the

event will be assumed to be treatment-emergent unless there is other evidence that confirms that the event was not treatment-emergent (e.g., the event end date was prior to the study drug start date).

All treatment-emergent AEs will be summarized overall, as well as by primary MedDRA SOC and Preferred Term. The SOCs will be presented in alphabetical order, and the PTs will be presented in alphabetical order within each SOC.

The number and percentage of subjects experiencing TEAEs will be summarized.

9.2.2 Adverse Event Overview

An overview of AEs will be presented consisting of the number and percentage of subjects experiencing at least one event for each of the following AE categories will be summarized for each treatment group:

- Any treatment-emergent AEs.
- Any COVID-19 related TEAEs.
- Any treatment-emergent AEs related to study drug according to the investigator.
- Any severe treatment-emergent AEs.
- Any serious treatment-emergent AEs.
- Any treatment-emergent AEs leading to discontinuation of study drug.
- Any treatment-emergent AEs leading to death.
- TEAEs of special interest (AESIs) (as defined in [Appendix B](#)).
- All deaths.
 - Any COVID-19 related deaths.
 - Occurring \leq 30 days after the last dose.
 - Occurring $>$ 30 days after the last dose.

Additional AEs may be considered for tabulation/summary based on recommendations from Clinical and Safety as deemed appropriate.

An overview of AEs will be presented based on data through Week 24 and Week 48. In addition, an overview of AEs through Week 48 per 100 patient-years of study exposure will be presented for the AE categories defined above. The number of TEAEs reported, the total number of years of study drug exposure, and the TEAE rate per 100 patient-years will be presented.

9.2.3 Treatment-Emergent Adverse Events by SOC and/or PT

Treatment-emergent adverse events, including COVID-19 related TEAEs, will be summarized by SOC and PT; by maximum relationship to study drug as assessed by the investigator (e.g., reasonable possibility or no reasonable possibility) and SOC and PT; by maximum toxicity grade and SOC and PT; and by subject number and SOC and PT. Specific adverse events will be counted once for each subject for calculating percentages, unless stated otherwise. In addition, if the same adverse event occurs multiple times within a subject, the maximum toxicity grade and level of relationship to investigational product will be reported.

In addition, TEAEs will be summarized by PT and sorted by decreasing frequency for the total active group.

TEAEs through Week 24, through Week 48 and through Week 48 per 100 patient-years of study exposure will be presented for the AE categories defined above.

9.2.4 Treatment-Emergent Adverse Events per Patient-Years of Exposure

Exposure-adjusted AEs through Week 48 per 100 patient-years will be provided, where AEs per 100 patient-years of exposure are defined as the number of AEs divided by the total exposure in 100 patient-years, i.e.,

$$100 * (\text{Number of TEAEs}) / (\text{Total Patient Years})$$

where total patient years is defined as the sum of the study drug exposure of all subjects, normalized by 365.25, and rounded to 1 decimal place. Note that one event per preferred

term per day per subject will be counted in the calculation of the number of AEs (i.e., a preferred term will not be counted twice on the same day for the same subject).

The TEAE through Week 48 per 100 patient-years will be provided for the following AE categories by SOC and PT:

- Any treatment-emergent AEs.
- Any COVID-19 related TEAEs.
- Any severe treatment-emergent AEs.
- Any serious treatment-emergent AEs.

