AbbVie may terminate this study prematurely at any time, either in its entirety or partially (discontinue 1 or more treatment groups), at any site. The study may be discontinued or terminated in case of an unacceptable risk, relevant toxicity, or a negative change in the benefit/risk assessment including the occurrence of AEs of which the character, severity, or frequency is new in comparison to the existing risk profile. In addition, data deriving from other clinical trials or toxicological studies which negatively influence the benefit/risk assessment might cause discontinuation or termination of the study. In the event the study is partially terminated, all subjects in the terminated arm(s) will be asked to return for a PD visit and to perform a 30-day follow-up phone call after the last dose of study drug. These subjects are not eligible for the LTE Study M20-186. The investigator may also stop the study at his/her site if he/she has safety concerns. If AbbVie terminates the study for safety reasons, AbbVie will promptly notify the investigator.

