7.4 Statistical Analyses for Safety

Safety analyses will be carried out using the Safety Analysis Set, which includes all subjects who receive at least 1 dose of study drug. Subjects will be grouped to the treatment actually received. Safety will be assessed by AEs, physical examination, laboratory assessments, ECGs, and vital signs. Frequency tables and lists of subjects with treatment-emergent adverse events (TEAEs) by preferred term as in the Medical Dictionary for Regulatory Activities (MedDRA®) dictionary, by system organ class, by severity, and by relationship to the study drug as assessed by the Investigator will be provided. The changes from Baseline in vital signs, physical examination results, and clinical laboratory values will be analyzed in a descriptive manner. Shift of laboratory values from Baseline to defined time points will be tabulated. Pre-treatment AEs will be summarized separately.

All TEAEs, SAEs, AEs leading to discontinuation, and AESI will be collected during the study. A TEAE is defined as an event with onset or worsening after the first study dose of study drug and within 30 days after the last dose of study drug administration. The number and percentages of subjects experiencing TEAEs will be tabulated using the MedDRA system organ class and preferred term. Summaries (including percentages and event per 100 patient-year) of SAEs, deaths, AEs leading to discontinuation, and AESI will be provided as well. For selected laboratory and vital signs parameters, mean change from Baseline and percentage of subjects with evaluations meeting pre-defined criteria for Potentially Clinically Important values will be summarized.

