ANA = antinuclear antibody; anti-dsDNA = anti-double stranded DNA; BILAG = British Isles Lupus Assessment Group; BTK = Bruton's tyrosine kinase; CBC = complete blood count; CLASI = Cutaneous Lupus Erythematosus Disease Area and Severity Index; DNA = deoxyribonucleic acid; ECG = electrocardiogram; FACIT = Functional Assessment of Chronic Illness Therapy; FSH = follicle stimulating hormone; HBc Ab = hepatitis B core antibody; HBs Ag = hepatitis B surface antigen; HCV Ab = hepatitis C virus antibody; HIV = human immunodeficiency virus; IgG = immunoglobulin G; IgM = immunoglobulin M; LupusQoL = Lupus Quality of Life questionnaire; Pain NRS = pain numerical rating scale; PBMC = peripheral blood mononuclear cell; PPD = purified protein derivative (tuberculin); PtGA = patient global assessment; RNA = ribonucleic acid; SF-36 = 36-Item Short Form Health Survey; SELENA = Safety of Estrogens in Lupus Erythematosus National Assessment; SJC = swollen joint count; SLEDAI = Systemic Lupus Erythematosus Disease Activity Index; TB = tuberculosis; TBNK = T lymphocytes, B lymphocytes, and natural killer lymphocytes; TJC = tender joint count; US = United States; WOCBP = women of childbearing potential

- * The 30-day follow up call will be calculated from the last study drug administration date/last visit for all subjects not entering the long-term extension LTE Study M20-186.
- a. A complete medical history and prior/concomitant therapy will be taken at Screening and will be updated at the Baseline Visit.
- b. The patient-reported outcome instrument should be completed prior to drug administration on Day 1 and prior to any discussion of adverse events or any review of laboratory findings. The subject should complete the questionnaires before site personnel perform any clinical assessments and before any interaction with site personnel has occurred to avoid biasing the subject's response.
- c. This is a clinician-reported outcome that is completed on the tablet.
- d. A complete physical examination will be performed during Screening and Study Day 1. Physical examinations at other visits can be symptom-directed.
- e. Urine pregnancy test will be performed locally as indicated in the table for all females of childbearing potential. The urine pregnancy test must be negative to receive study drug. If any urine pregnancy test is positive, a serum pregnancy test will be performed by the central laboratory.

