6.0 Study Drug Duration and Compliance

6.1 Study Drug Duration

The duration of exposure to study drug will be summarized by each treatment group using the Safety Analysis Set population.

- Duration of exposure = the last study drug dose date – the first study drug dose date + 1.

For the Safety Analysis Set, duration of treatment will be summarized for each treatment group and for all investigational study drug dose groups combined. The duration of treatment is defined for each subject as last dose date minus first dose date + 1. Duration of treatment will be summarized using the number of subjects, mean, standard deviation, minimum, median and maximum for duration of Study M19-130. In addition, the number and percentage of subjects exposed to study drug will be summarized for the following exclusive duration intervals:

- ≥ 1 day
- ≥ 29 days
- ≥ 57 days
- ≥ 85 days
- ≥ 113 days
- ≥ 141 days
- ≥ 169 days
- ≥ 197 days
- ≥ 225 days
- ≥ 253 days
- ≥ 281 days
- ≥ 309 days
- ≥ 337 days

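### AE rates per 100 patient-years count events for 30 days after the last dose but divide by dosing time only, which inflates rates most in arms that stop early

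*SAP*

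**What the plan says.** - **Events.** SAP 9.2.1 counts any AE with onset from the first dose and "within 30 days after the last dose administration of the study drug in M19-130". Protocol 7.4 sets the same limit: "within 30 days after the last dose of study drug administration".
- **Person-time.** SAP 9.2.4 multiplies the number of such events by 100 and divides by total patient-years, where "total patient years is defined as the sum of the study drug exposure of all subjects". SAP 6.1 defines exposure: "Duration of exposure = the last study drug dose date – the first study drug dose date + 1". Nothing adds the 30 post-drug days, and interruptions are not subtracted.
- **Reporting period.** "Exposure-adjusted AEs through Week 48 per 100 patient-years will be provided" (SAP 9.2.4). The SAP does not say whether this caps the onset date.
- **Who has post-drug follow-up.** Under Protocol 5.5, subjects in a terminated arm are asked to attend a premature discontinuation visit and take a 30-day call. "These subjects are not eligible for the LTE Study M20-186". In Protocol Appendix D the 30-day call is "for all subjects not entering the long-term extension LTE Study M20-186".
- **Who is in the tables.** SAP 9.1 keeps terminated and continued groups in the safety analyses. The exception is mean change in laboratory values and vital signs, which is given for continued groups only.

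**The concern.** The numerator covers up to 30 more days per subject than the denominator. If every subject had the same exposure, each arm would be inflated by the same factor and comparisons would survive. This design does not guarantee that. Whole arms may stop after the interim analysis, and the subjects in them have both the full post-drug window and the shortest denominators.

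Rates per 100 patient-years are the SAP's means of comparing safety across arms with unequal exposure. They feed the AE overview (SAP 9.2.2), the SOC and PT tables (9.2.3, 9.2.4) and the AESI summaries (9.2.6), in a trial meant to choose doses for further development. A mismatch that grows as exposure shrinks can make a terminated regimen look less safe than it was.

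**Working it through.** The documents state no AE rate, exposure total or discontinuation rate, so there is no planned figure to reproduce.

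**Inputs from the documents:** a 30-day window after the last dose (SAP 9.2.1); exposure T = last dose − first dose + 1 (SAP 6.1); 48 weeks = 336 days of planned treatment; 65 subjects per arm (SAP 2.4).

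**Assumptions:** a constant event hazard unless stated; a continued arm in which 10% or 30% stop at Week 12 (84 days) and the rest reach 336 days; a terminated arm in which every subject has 36, 24 or 16 weeks of exposure (252, 168 or 112 days) and none roll over.

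**Step 1, one subject.** Reported rate / window-matched rate = (T + 30)/T = 1 + 30/T.
- T = 252: 1.119
- T = 168: 1.179
- T = 112: 1.268
- T = 84: 1.357
- T = 336: 1.089 if onset is not capped at Week 48, and 1.000 if it is

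**Step 2, lower hazard off drug.** At half the on-drug hazard, the inflation over the on-drug rate is 1 + 0.5 × 30/T: 1.089 at 168 days and 1.179 at 84 days.

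**Step 3, what a table would show.** Take 65 subjects with 168 days each and an assumed true rate of 200 per 100 patient-years.
- Denominator: 65 × 168/365.25 = 29.9 patient-years
- Events counted: 2 × 65 × 198/365.25 = 70.5
- Reported rate: 236 instead of 200

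**Step 4, the continued arm.** Mean exposure is 0.9 × 336 + 0.1 × 84 = 310.8 days, or 0.7 × 336 + 0.3 × 84 = 260.4 days.

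| Reading | 10% stop early | 30% stop early |
|---|---|---|
| No Week 48 cap on onset | 340.8/310.8 = 1.097 | 290.4/260.4 = 1.115 |
| Onset capped at Week 48 | (310.8 + 0.1 × 30)/310.8 = 1.010 | (260.4 + 0.3 × 30)/260.4 = 1.035 |

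**Step 5, terminated / continued ratio when the true ratio is 1.**
- No cap: from 1.119/1.115 = 1.00 to 1.268/1.097 = 1.16
- Cap: from 1.119/1.035 = 1.08 to 1.268/1.010 = 1.26

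The cap makes the contrast larger because completers lose their post-drug days while early stoppers keep theirs. The value of 1.00 arises where the two arms have nearly the same mean exposure (252 and 260.4 days).

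**The case against.** The best defence is that these tables run through Week 48 and rollover occurs at Week 48. On the natural reading, completers then contribute no post-drug days and no LTE events. That stands for completers. It does not help early stoppers, and Step 5 shows that it widens the gap between arms.

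Several further points limit the consequence, and they are fair:
- No test is specified on these rates. The Fisher's exact test in Operations Manual 4.2 uses numbers and percentages of subjects, which do not depend on this denominator.
- SAP 9.2.2 shows the event count, exposure years and rate together, so the convention is visible.
- Dividing by on-drug time is a familiar convention, and it does little harm when exposure patterns match.
- The SAP treats partial termination as conditional (8.1, 8.4.2). Protocol 7.5 says a committee decided which groups to continue, but the documents do not say which arms stopped, if any.
- The event hazard may fall once drug is stopped, which shrinks the inflation (Step 2).

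A reader might infer more: that the open-ended window runs into LTE dosing, so LTE events would be credited to the wrong M19-130 arm. The documents do not support this. The LTE is a separate protocol, rollovers have no M19-130 30-day call, and nothing says that post-rollover events enter the M19-130 data. A rollover subject also has only one M19-130 arm. What remains is that SAP 9.2.1 states no cut at the first LTE dose and that the through-Week-48 label is undefined.

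**Conclusion.** The mismatch is on the face of the SAP and should be corrected. For a subject who stops early it overstates the rate by about 30/exposure, and by about half of that if the off-drug hazard is half the on-drug hazard. Between a terminated and a continued arm with equal true rates, the reported ratio would be about 1.00 to 1.16 without a Week 48 cap and about 1.08 to 1.26 with one. These ranges rest on assumed exposures, a constant hazard and full 30-day follow-up of early stoppers. Arms with similar exposure patterns are inflated equally, so ratios between them hold.

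A single headline ratio would claim too much. With assumed means of 200 days (terminated) and 300 days (continued, 70% rolling over), the ratio is 1.15/1.03 = 1.12 if rollovers contribute no post-drug days, and 1.15/1.10 = 1.045 if they contribute all 30. The two assumptions exclude each other, and the documents do not choose between them.

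The point concerns safety reporting only. Percentages of subjects with events and the efficacy analyses are untouched.

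**What to change.** For every table per 100 patient-years, define one interval and use it for both events and person-time. It should run from first dose to the earliest of:
- last dose + 30 days
- last contact
- the day before the first LTE dose
- the Week 48 cut-off

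State that the through-Week-48 label caps onset, and define the cut-off (a study day or the Week 48 visit). Show time at risk beside the study drug exposure years that SAP 9.2.2 requires.

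Change numerator and denominator together. Suppose events were cut at the first LTE dose with the denominator left alone, no Week 48 cap, and 90% of completers rolling over (assumed). The continued-arm factor would fall to 1.018 to 1.043, and the ratio between arms would become about 1.07 (1.119/1.043) to 1.25 (1.268/1.018). With matched intervals and a constant hazard the factor is 1.00 in every arm.

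The cost is an added person-time derivation, an extra patient-years column, first LTE dose dates from Study M20-186, and rates slightly lower than under the present convention. The matched rate also averages on-drug and off-drug days. At half the hazard off drug it would be (112 + 15)/142 = 0.89 of the on-drug rate for a subject with 112 days of exposure, and 1.00 for a completer cut at Week 48. A supportive on-drug rate, counting events from first to last dose over the existing exposure, would show this and needs no new data.
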